3.3 Subject recruitment information

CCI [REDACTED]	[REDACTED]
[REDACTED]	[REDACTED]
[REDACTED]	[REDACTED]
[REDACTED]	[REDACTED]
[REDACTED]	[REDACTED]

3.4 Subject enrolment and randomization

CCI [REDACTED]
[REDACTED]
[REDACTED]

- [REDACTED]
[REDACTED]
- [REDACTED]
[REDACTED]
[REDACTED]
[REDACTED]
[REDACTED]
- [REDACTED]
- [REDACTED]
[REDACTED]

[REDACTED]
[REDACTED]
[REDACTED]

[REDACTED]
[REDACTED]
[REDACTED]

[REDACTED]

[REDACTED]
[REDACTED]
[REDACTED]
[REDACTED]

CCI

3.5 Procedures for handling incorrectly enrolled or randomized subjects

Subjects who fail to meet the eligibility criteria should not, under any circumstances, be enrolled or receive study medication. There can be no exceptions to this rule. Subjects who are enrolled, but subsequently found not to meet all the eligibility criteria must not be randomized or initiated on treatment, and must be withdrawn from the study.

Where a patient does not meet all the eligibility criteria but is randomized in error, or incorrectly started on treatment, the following steps need to be taken:

- The Investigator or monitor should inform the AstraZeneca study physician immediately, ensuring patient safety must always be the number one priority.
- Study Treatment must be discontinued in all cases where continued treatment is deemed to pose a safety risk to the patient. A discussion should occur between the AstraZeneca study physician and the investigator, a decision may be reached that whether to continue or discontinue the patient from study treatment. The AstraZeneca study physician must ensure all decisions are appropriately documented.
- In those cases where continuation of study therapy is judged not to present a concern related to safety and disease management, the rationale for continuing study therapy must be clearly documented. The patient should continue follow up in accordance with defined study procedures.

3.6 Methods for assigning treatment groups

CCI

[Redacted content]

3.8 Methods for unblinding

Individual treatment codes, indicating the treatment randomisation for each randomised subject, will be available to the Investigator(s) or pharmacists from the IVRS/IWRS. Routines for this will be described in the IVRS/IWRS user manual that will be provided to each centre.

<<(JP) Replace the above paragraph with: Individual treatment codes, indicating the treatment randomisation for each randomised subject, will be available to the Investigator(s) or pharmacists, and the personnel who are independent to the study evaluation at the Patient Safety Department, AstraZeneca from the IVRS/IWRS.>> (End JP)

The treatment code should not be broken except in medical emergencies when the appropriate management of the subject requires knowledge of the treatment randomisation. The Investigator documents and reports the action to AstraZeneca, without revealing the treatment given to subject to the AstraZeneca staff.

AstraZeneca retains the right to break the code for SAEs that are unexpected and are suspected to be causally related to an investigational product and that potentially require expedited reporting to regulatory authorities. Treatment codes will not be broken for the planned analyses of data until all decisions on the evaluability of the data from each individual subject have been made and documented.

3.9 Restrictions

- All patients will visit the clinic fasting in the morning, between 6 a.m. to 10 a.m. Patients will be instructed to abstain from all food and beverages for 8 hours prior to each clinic visit (except for Visit 1). Drinking water is allowed.
- Patients should not drink alcohol within 24 hours prior to each visit and should not use tobacco/nicotine within 12 hours prior to each visit.
- Patients should bring all their medications and IP to the site.
- Anti-hypertensive medication can be taken with a glass of water after completion of BP and body weight measurements.
- Medications including IP should be taken after visit samples and examinations have been performed. Anti-hyperglycemic drugs should be taken in connection with a meal.
- Antiepileptic drugs and antibiotics shall be taken as prescribed.
- Women must immediately contact the Investigator if they suspect they might be pregnant and if they have changed or plan to change their birth control method.

If a patient arrives for a visit without having followed the above instructions, the entire visit should be rescheduled (within the allowed time-window, if possible).

Donation of blood or blood products to a blood bank is not allowed during participation in the study. Prohibited and restricted concomitant medications are listed in Section 7.7.

3.10 Discontinuation of investigational product

Patients may be discontinued from IP in the following situations:

- Patient decision. The patient may, at any time, discontinue study treatment, without prejudice to further treatment. Patients who choose to discontinue study treatment are expected to continue in the study until the closing of the study.
- Safety reasons as judged by the Investigator, by or an AZ representative.
- Severe non-compliance to protocol as judged by the investigator and/or AZ

Subjects MUST discontinue study treatment (investigational or non-investigational treatment) for any of the following reasons:

- Any clinical AE, laboratory abnormality or inter current illness which, in the opinion of the Investigator, indicates that continued participation in the study is not in the best interest of the subject.
- Pregnancy
- Termination of the study by AstraZeneca.
- Loss of ability to freely provide consent through imprisonment or involuntarily incarceration for treatment of either a psychiatric or physical (e.g., infectious disease) illness.
- Protocol-defined major hypoglycemia episodes.
- Liver criteria:

ALT and/or AST >3 times the upper limit of normal (ULN) and concomitant TB >2 times ULN confirmed at a repeated measurement at the central laboratory (which should be obtained within 3 days, whenever possible, following receipt of the initial laboratory results)

ALT and/or AST >8 times ULN confirmed at a repeated measurement at the central laboratory (which should be obtained within 3 days, whenever possible, following receipt of the initial laboratory results)

ALT and/or AST >5 times ULN confirmed at the central laboratory and sustained over a period of 14 days or more

(See Appendix D Algorithm on Management of Sustained Elevated Liver Safety Abnormalities for further details)

- Acute renal insufficiency or worsened chronic renal insufficiency based on sustained ≥ 1.5 times increase in baseline s-creatinine (see page 56 Discontinuation Guidelines due to Acute Kidney Injury).

Clinical indications for discontinuation because of hypoglycemia may include the following:

- Multiple occasions of episodes outlined below that, in the opinion of the Investigator, indicate that continued treatment with study therapy is not in the best interest of the patient. This includes, but is not limited to:
 - Symptoms suggestive of hypoglycemia (e.g, sweating, shakiness, increased heart rate, confusion, dizziness, light-headedness, or hunger) in the absence of environmental factors known to contribute to hypoglycemia (ie, excess physical activity, concurrent illness, or missed or delayed meal)

and/or

- Documented finger stick glucose values < 54 mg/dL (< 3.0 mmol/L).

3.10.1 Discontinuation Guidelines due to Protocol-Defined Major Hypoglycemia Episode or Recurrent Non-Major Hypoglycemia Episodes

Subjects will be discontinued from study medication if they experience severe and/or frequent hypoglycemia episodes, defined as more than one major episode or recurring non-major episodes in the event where the possibility of down-titration of insulin and/or oral anti-diabetic medication(s), (other than blinded study medication) and/or other contributing factors (e.g., excessive physical activity) have been evaluated and corrected. ***NOTE: Dose titration of blinded study medication is not permitted at any time during the study.***

- A Major Hypoglycemia Episode is defined as a symptomatic episode which meets **all** of the following criteria:
 - External (the 3rd party) assistance due to severe impairment in consciousness or behaviour.
 - Capillary or plasma glucose value of < 3 mmol/L (< 54 mg/dL)
 - Prompt recovery after glucose or glucagon administration
- Recurring Non-Major Episodes are defined as any recurrent hypoglycemia episodes, as determined by the Investigator, not meeting the definition of Major Episodes.

It is the Investigator's clinical assessment whether subjects who experience non-recurrent and non-major episodes of hypoglycemia should be discontinued from study medication.

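### The mandatory hypoglycaemia stopping rule in Section 3.10 does not match Section 3.10.1, so a patient with exactly one major episode can be read as having to stop or as below the threshold.

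*Protocol*

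**What the plan says.** Section 3.10 opens its mandatory list with "Subjects MUST discontinue study treatment (investigational or non-investigational treatment) for any of the following reasons". One entry is "Protocol-defined major hypoglycemia episodes", with nothing further. After that list, a separate paragraph begins "Clinical indications for discontinuation because of hypoglycemia may include the following" and describes multiple occasions of suggestive symptoms and/or low finger-stick values that, in the Investigator's opinion, make continued treatment not in the patient's best interest.

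Section 3.10.1 is headed "Discontinuation Guidelines due to Protocol-Defined Major Hypoglycemia Episode or Recurrent Non-Major Hypoglycemia Episodes". Its first sentence says subjects will be discontinued for severe and/or frequent hypoglycaemia, "defined as more than one major episode or recurring non-major episodes". A condition follows, beginning "in the event where the possibility of down-titration of insulin and/or oral anti-diabetic medication(s": those adjustments and/or other contributing factors are to have been evaluated and corrected. The section then gives an event-level definition ("A Major Hypoglycemia Episode is defined as a symptomatic episode which meets" all of three criteria) and says recurring non-major episodes are determined by the Investigator. It closes by leaving to the Investigator "whether subjects who experience non-recurrent and non-major episodes of hypoglycemia should be discontinued from study medication". Section 6.3.8 defines a major event by the same elements, again without a count.

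**The concern.** The rule is labelled mandatory, so a site should be able to tell from the text alone when it applies. Here the list and the detailed section can lead two careful readers to different actions for the same patient.

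The situation is not remote. Background insulin and oral agents, including sulfonylureas, continue during the study. Exclusion criterion 8 removes only patients with two or more major events in the prior 3 months, so a patient with one such event may enter. About 100 sites will read the text, and Section 6.8.2 marks a data monitoring committee as not applicable.

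At stake are uniform protection of patients and uniform recording. A site that follows one section could be recorded as deviating from the other. Under Section 3.10.5, stopping study drug also brings the Week 24 procedures forward to the time of discontinuation, so the visit record would depend on which section the site had followed.

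**Working it through.** No arithmetic applies: the protocol gives no hypoglycaemia event rate and the point depends on no sample-size or power figure. The check is to apply each section to the same patient.

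**Step 1. Where the count comes from.** The 3.10 list item relies on the protocol's definition of a major episode. That definition, in 3.10.1 and again in 6.3.8, describes one episode and contains no number. The requirement of more than one appears only in the first sentence of 3.10.1, so it cannot be imported into 3.10 through the definition.

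**Step 2. Whether 3.10 points to 3.10.1.** In the same list, the liver item refers the reader to an appendix and the renal item to the acute kidney injury guidelines. The hypoglycaemia item refers nowhere.

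**Step 3. Whether 3.10.1 agrees with itself.** The heading has a major episode in the singular and attaches recurrence only to non-major episodes. The first sentence requires more than one major episode. The closing sentence reserves for judgement only episodes that are both non-recurrent and non-major. Taken alone, 3.10.1 therefore neither requires stopping after a single major episode nor assigns that case to the Investigator.

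**Step 4. The rule applied to four patients.**

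- *Exactly one major episode.* 3.10: must stop, if one episode is enough for the list item. 3.10.1: threshold not met, so stopping is not required.
- *Two or more major episodes, other factors not yet corrected.* 3.10: must stop, even if the plural is taken to mean more than one. 3.10.1: must stop if the correction condition attaches only to recurring non-major episodes; not yet required if it attaches to both limbs of the sentence. The grammar allows either.
- *Recurring non-major episodes, other factors corrected.* 3.10: a possible indication, on the Investigator's opinion. 3.10.1: will be discontinued.
- *One isolated non-major episode.* 3.10.1 leaves this expressly to the Investigator, and nothing specific in 3.10 requires stopping. No conflict.

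The first case is the main inconsistency. The second and third are secondary ambiguities.

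**The case against.** The best defence is that the 3.10 item is plural and does not say that one episode suffices. Section 3.10 can be read as a summary list and 3.10.1 as the operative rule, much as the short renal item is spelled out in 3.10.2; a heading is a label rather than a rule. This reading is available, and it is why the text does not support saying flatly that one section compels stopping and the other does not. It does not remove the problem: the renal item carries a pointer and this one does not, the definition is per episode, and the heading and closing sentence of 3.10.1 fit its threshold poorly.

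It is also fair that the correction condition may attach only to recurring non-major episodes, in which case the plural item and the major limb of 3.10.1 agree. That is an ambiguity to settle, not proof of conflict. Section 3.10 has a related but different qualifier of its own, the absence of environmental contributors, without a down-titration step.

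The contrast for non-major episodes is softened because recurrence in 3.10.1 is determined by the Investigator, and the first mandatory item in 3.10 already requires stopping whenever the Investigator judges continuation not in the subject's best interest. For the same reason no patient lacks a stopping route. These routes do not settle what is mandatory.

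A reader might infer that the Week 24 comparisons are affected. The protocol does not show this. Section 3.10.5 asks patients who stop drug to complete all scheduled visits through Week 27, and the exclusion stated in Sections 8.3 and 8.6.1 is of results after glycaemic rescue; no exclusion of data after drug discontinuation is stated. A reader might also want a number of affected patients, but any figure would rest wholly on an assumed event rate.

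**Conclusion.** The point stands in limited form. The mandatory list in 3.10, the heading of 3.10.1 and the text of 3.10.1 do not state one rule, and a patient with exactly one major episode is where the readings part. The scope of the correction condition and the status of recurrent non-major episodes are secondary uncertainties, and the first of these remains even if the plural in 3.10 is taken to mean more than one.

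The size is qualitative: inconsistent application of a mandatory safety rule across sites, and inconsistent recording of drug discontinuations. The conclusion assumes only that sites act on the text as written. It is worth correcting because the rule is mandatory and the correction is cheap, not because a shift in any efficacy estimate has been shown.

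**What to change.** Reconcile the 3.10 list item, the 3.10.1 heading and the 3.10.1 text into a single rule that states:

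- the number of major episodes that makes stopping mandatory;
- whether the correction condition applies to major episodes, to recurring non-major episodes, or to both;
- whether stopping for recurrent non-major episodes is mandatory or at the Investigator's discretion.

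Add a cross-reference from the 3.10 item to 3.10.1. The closing sentence of 3.10.1 should then match, so that every type of episode is placed either under the rule or under judgement. Which rule is clinically right is for the sponsor to decide. The cost is wording in a protocol amendment and notice to sites; no change to sample size, visits or analysis follows.

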3.10.2 Discontinuation Guidelines due to Acute Kidney Injury (AKI)

For patients with signs of deterioration in renal function, additional monitoring needs to be conducted. Any patients with ≥ 1.5 x baseline serum creatinine increase needs to be scheduled for a new serum creatinine test within 4 days whenever possible.

- If the new serum creatinine value is ≥ 1.5 x basal level, the patient should be evaluated for any suspected new, temporary and reversible cause of renal dysfunction, e.g. concurrent use of NSAIDs, antibiotics, or other medications known to affect creatinine clearance; volume depletion; urinary tract infection, and obstructive uropathy.
 - If there is no suspected cause of the acute drop in renal function, the subject must permanently discontinue study medication and the Sponsor is notified. The investigator will follow the subject until the event has resolved or stabilized.
 - If there is a suspect reversible cause, the following actions should be taken:
 - Study medication should be withheld.
 - The suspected cause of renal dysfunction should be identified and corrected.
 - Serum creatinine should be checked again after approximately one week:
 - ◆ If serum creatinine is still ≥ 1.5 x baseline level:
 - The subject must permanently discontinue study medication and the Sponsor is notified. The Investigator will follow the subject until the event has resolved or stabilized
 - ◆ If serum creatinine is < 1.5 x baseline level:
 - Study medication can be resumed.
 - Serum creatinine should be checked after approximately one week
 - The subject may continue in the study and will be followed according to the protocol. Additional monitoring of serum creatinine may be performed according to the local practice or Investigator's judgment.

3.10.3 Rescue Due to Lack of Glycemic Control in the Treatment Period

Rescue Medication

Patients with lack of glycemic control during the 24 week treatment period may be eligible to receive open-label rescue medication in addition to their blinded treatment in order to treat ongoing hyperglycemia. Patients may receive open-label rescue medication added on to, but not as a replacement for, their current study medication regimen. Rescue medication in this

protocol refers to any approved, appropriate anti-diabetic agent, except SGLT2-inhibitors, GLP-1 agonists or DPP4 inhibitors, in accordance with the approved label and conventional standards of care. Open-label rescue medication is to be titrated as needed to obtain adequate glycemic control.

During the treatment period, all rescue decisions will be based on central laboratory FPG and confirmatory FPG results. If patients meet the protocol-specified glycemic criteria based on FPG, they will be recommended for open-label rescue medication.

Patients in the follow-up phase will not need to adhere to the protocol defined rescue criteria, and may have their anti-diabetic regimen adjusted at the Investigator's discretion, except to start treatment with a SGLT2 inhibitor, a GLP1 agonist or a DPP4 inhibitor.

The sections and tables listed below define the lack of glycemic control criteria for initiation of open-label rescue medication.

Protocol-Defined Lack of Glycemic Control Criteria for Initiation of Open-Label Rescue Medication

Pre-specified glycemic criteria (see Table 1 below), based upon central laboratory FPG and confirmatory, repeat FPG, have been established during the 24 week treatment period, starting at Week 4 and up to Week 24 visits, to determine eligibility for open-label rescue medication initiation/titration.

Table 1 Lack of Glycemic Control Criteria for Initiation of Open-Label Rescue Medication

Visit Label	Central Laboratory FPG
From Week 4 to Week 12 (excluding week 12)	FPG > 240 mg/dL (13.3 mmol/L)
From Week 12 to Week 24 (excluding Week 24)	FPG > 200 mg/dL (11.1 mmol/L)

Patients with a central laboratory FPG value meeting the lack of glycemic control criterion at a pre-specified visit will be scheduled for a follow-up visit (within 3 - 5 days) to obtain a second central laboratory FPG value and review the patient's glucose meter readings. If the repeat central laboratory FPG value still meets the criterion, the patient will receive rescue medication.

Irrespective of study visit number, patients who meet rescue criteria in the treatment period must first complete the Week 24 visit procedures (within 5 days whenever possible) before being rescued to ensure that important trial endpoint measurements are collected.

Following completion of the Week 24 "Rescue" visit, rescued patients will be administered open-label rescue medication in addition to their blinded study medication. Rescued patients will then continue in the treatment period according to their original visit schedule. Patients who received a first rescue medication, who subsequently fulfil lack of glycemic control criteria, may have other rescue medications added or substituted, according to Investigator judgment, without repetition of rescue visits.

3.10.4 Guidelines with regard to changes in insulin dose

Each subject's baseline insulin therapy should remain unchanged wherever possible throughout the double-blind treatment period. The stable insulin regimen aims to continue insulin as it was being used by the subject at enrollment and lead-in, with no changes to insulin type and with as few changes in insulin dosage as possible. A stable insulin regimen is pivotal, because it makes it possible for the study to measure any differences in glycaemic control between the active treatment arms and the placebo arm. During the double-blind treatment period, a few subjects will experience poor glycaemic control, as measured by increased fasting plasma glucose measurements from the central laboratory during study visits. When glucose measurements exceed certain limits (as specified), the subject will be "rescued".

Up-titration in insulin dose is not allowed, unless fasting blood glucose rescue criteria is fulfilled or if insulin requirement has increased only temporarily, e.g., due to an infection and the increase in insulin dose is ≤ 10 percent of the baseline level after 1 week. If lasting increase in insulin dose is made i.e. the insulin dose is still >10 percent higher than the baseline level 1 week after up-titration, the subject shall be handled as administration of anti-diabetic rescue medication and be treated as "rescued" (i.e., the patient must complete the Week 24 visit procedures, as outlined in section 4.5.7 and the patient will continue in the treatment period according to their original visit schedule.

Down-titration of insulin is allowed only as necessary to prevent low blood glucose or hypoglycemia.

3.10.5 Procedures for discontinuation of a subject from investigational product

If a subject was withdrawn before completing the study, the reason for withdrawal must be entered on the appropriate case report form (CRF) page.

At any time, subjects are free to discontinue investigational product or withdraw from the study (i.e., investigational product and assessments – see Section 3.11), without prejudice to further treatment. A subject that decides to discontinue investigational will always be asked about the reason(s) and the presence of any adverse events. If possible, they will be seen and assessed by an Investigator(s). Adverse events will be followed up (See Section 6); *<<diary cards, questionnaires (e.g., for patient reported outcomes)>>* and all study drugs should be returned by the subject.

All patients who discontinue study drug will be asked to remain in the study for FU and complete all scheduled study visits through Week 27. At the time of discontinuation the Week 24 (Visit 9) procedures will be performed. Patients will then complete all scheduled study visits and procedures. Patients unable or unwilling to return for scheduled visits as part of follow-up will have the opportunity to receive follow-up via telephone calls placed by the site mainly to review safety and concomitant medications. The only exception to this procedure is when a patient withdraws consent for all study procedures or loses the ability to consent freely (i.e., is imprisoned or involuntarily incarcerated for the treatment of either a psychiatric or physical illness).

If a subject is withdrawn from study, see Section 3.11.

